**NCT02698163**

**Study Protocol in Submitted UCLA IRB#15-002015 (March 4th, 2020)**

## **Summary:**

Non-surgical root canal therapy (RCT) represents a standard of treatment that addresses infected pulp tissue in teeth and protects against future infection while preserving the tooth for the patient. RCT involves removing dental pulp comprising blood vessels and nerve tissue, followed by the placement of filler material to occupy the naturally occurring space where the pulp was removed. Currently, standard of care treatment for RCT utilizes gutta-percha (GP) as the root canal filling material. Tooth extraction is necessary if the RCT fails or if the tooth fractures. The need for extraction after failed RCT might be reduced by increasing the strength of the canal filling material closer to that of dentin. Nanodiamonds (NDs) may offer unique advantages due to their favorable properties, particularly for dental applications. In this prospective pilot study, we will utilize gutta-percha modified with nanodiamonds 5 wt % (NDGP) as the root canal filling material. Our research group has previously demonstrated NDGP's improvement in tensile strength compared to those of gutta-percha. We hypothesize that NDGP will not have a negative effect on clinical outcome for the patient compared to the GP. Additional potential positive benefits include decrease in void space and better clinician handling of NDGP during the canal filling procedure. NDGP with its increased mechanical properties, potential decrease in void space between the NDGP and the tooth's root, and the ease of handling by clinician of NDGP during vertical obturation procedure may result in a decrease in the pain experienced by the NDGP patients compared to those experienced by the control (GP) patients. Patients will be recruited and randomized into two RCT filler material patient groups for this study: 15 patients for the control, 15 patients with NDGP. For all the patients into the control arm of the study, the root canals will be filled with GP at the bottom third up to and including the top third, using a standard procedure involving vertical condensation obturation. For all the patients into the treatment arm of the study, the root canals will be filled with GP at the bottom third, NDGP in the middle third, and again with GP at the top third, using the vertical condensation obturation technique. The tooth will be restored with a crown for posterior teeth, or a composite filling for anterior teeth. There will ideally be a total of four visits: consultation appointment (~1 hour), RCT appointment (~2-3 hours), 6 month follow-up appointment (~1 hour), and 1 year follow-up appointment (~1 hour). Additional follow-up appointments (~1 hour) prior to the 6 month and 1 year follow-up appointments may be required in the event of infection or persistent pain of the root canal. Patient data will be categorized by age, weight, gender, and use of other drugs which may alter the pain assessment and pilot study success indicators. This study investigates a new type of filler, gutta-percha modified by the addition nanodiamond material (NDGP), which may be stronger and prevent complications of RCT such as tooth fracture to improve treatment outcomes.

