Follow-up examination consists of updating the general and endodontic history of the treated teeth upon clinical and radiographic examination. All patients will be interviewed and examined by one individual from the study team to remain consistent and reduce sources of bias from involving multiple individuals. Extraoral examination will be performed, which includes palpation of masticatory, neck and shoulder muscles, lymph nodes, and palpation of the temporomandibular joint for tenderness or any abnormalities. Clinical examination of the treated teeth will be carefully noted in detail, including the following details: (1) tenderness to percussion of the tooth, (2) tenderness to palpation of adjacent soft tissues, (3) presence of sinus tract or abscess, (4) periodontal probing depths around the tooth, (5) type/presence of coronal seal and restoration. Further examination of the restoration will be done and classified into the following three categories: (A) visual or tactile exposure of root filling material, (B) clinical or radiographically detected marginal discrepancy but without visual or tactile exposure of root filling to the oral cavity, (C) satisfactory coronal restoration with good retention and margins.

The radiographs will be taken digitally with size 1 or 2 XDR Digital Intraoral sensors (XDR Radiology, Los Angeles, CA, USA). The images will then be transmitted and analyzed by the XDR program.

If the patient feels persistent discomfort from the treated tooth at follow-up, periapical radiographs at different horizontal angles will be taken to detect any radiolucent pathology that may be superimposed upon the root. If the patient is pregnant at the time of the follow-up appointment, the radiographic examination will be deferred until after delivery.

All the preoperative, immediate post-obturation, and follow-up radiographs will be viewed on the computer screen with the "caries" and "endo" detection feature and magnifying viewer tools in the XDR program as needed. The preoperative periapical status of each root will be classified into three categories: (1) intact periodontal ligament, (2) widened periodontal ligament or (3) periapical lesion. The diameter of the lesion preoperatively and at follow-up was measured using the measuring ruler tool in the XDR program. The diameter for widened periodontal ligament will be recorded as

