0.5 mm. The quality of previous treatment will be judged satisfactory if a well-condensed root filling extends to within 2 mm of the radiographic root apex.

Treatment success will be evaluated based on two outcome measurements: (1) absence of apical periodontitis via clinical and radiographic evaluation, (2) tooth survival.

The assessment of treatment success will strictly be defined as absence of pain, clinical signs of inflammation or swelling, and radiographic measures of complete healing (i.e. presence of normal periodontal ligament space, intact lamina dura, etc). A potential consideration for treatment success will also include aspects from the patient such as the absence of pain and/or clinical signs of inflammation or swelling and radiographic measures of complete healing or *incomplete healing* (i.e. reduced size of periapical lesion without normal periodontal ligament space width).

In some of these cases where the failure is not due to an iatrogenic perforation, a secondary RCT, also called non-surgical endodontic retreatment, might be indicated to resolve any pulp tissue that may have been left behind. A secondary RCT may also be necessary if there is failure of primary RCT due to narrow or curved canals were not treated during the initial procedure, complicated canal anatomy went undetected in the first procedure, placement of the crown or other restoration was delayed following the endodontic treatment, inadequate seal during primary RCT and a radiolucency that still persists or expands. Furthermore, a secondary RCT is indicated if any infection from primary RCT causing persistent pain and or periapical lesion seen in the radiograph. This secondary RCT will still be done with NDGP in the middle third of the root, as the cause of failure in the first place would have been because of regular in-tact gutta percha extruding from the apex or insufficient instrumentation.

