The root canal therapy (RCT) procedure has potential risks and complications associated with the procedure: possible pain swelling, separation of instrument, perforation, fracture/crack, requirement for permanent restoration, and extraction of tooth if persistent infection is observed. If the tooth is indicated for an extraction instead, the extracted tooth will be evaluated for other potential causes of failure (eg. cracked tooth, missed extra canals, difficult canal anatomy, etc.). Extractions should be considered upon the identification of a fractured and cracked tooth during an apicoectomy. After the root canal therapy, if pain or pressure persists for more than a few days after the RCT, the endodontist would need to evaluate the prognosis of the tooth and determine whether the tooth is viable or needs extraction due to inadequate infection control of the canal or damage to tooth structure during the RCT. An extraction may also be indicated several years after the RCT due to persistent infectious bacteria or microleakage of the endodontically treated tooth. Other indications for extractions include perforations, coronal breakdown, or periodontal disease. If a tooth were to be extracted due to endodontic problems, such as persistent pain, swelling, sinus or periapical lesion, the treatment will be considered as a failed outcome. Tooth extraction without any information on postoperative periapical status will be excluded from analysis. We have to keep in mind that even conventional RCTs do not have a 100% success rate. Most studies say that primary RCTs have about a 86% success rate - so when taking that into consideration, we cannot assume that if the procedure fails, it is due to the NDGP material.

Customized forms, recorded by endodontic postgraduate students, will be used for recording follow-up information and radiographic assessments. The patient's medical conditions will be self-reported onto a standard medical history form at the first appointment and will be verified and updated by interview prior to the both arms of control and treatment and at the follow-up appointment. While all conditions reported by the patient will be recorded, only those that will be common among the patients or previously reported to have significant association with treatment outcome will be further analyzed.

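### Failed teeth are to be refilled with the experimental filler because the cause of failure is presumed in advance, with no stated link between assessing the tooth and choosing the material

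*Combined protocol and SAP*

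**What the plan says.** The paragraph on secondary RCT in the Study Protocol section first says when a repeat treatment may be indicated. It starts from cases "where the failure is not due to an iatrogenic perforation". It then names residual pulp, narrow or curved canals left untreated, anatomy missed the first time, late placement of the crown or restoration, and "inadequate seal during primary RCT and a radiolucency that still persists or expands". Infection with persistent pain or a visible lesion is a further indication.

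The filler rule follows: "This secondary RCT will still be done with NDGP in the middle third of the root, as the cause of failure in the first place". The reason given, fixed ahead of any case, is that the failure "would have been because of regular in-tact gutta percha extruding from the apex or insufficient instrumentation". The rule names no arm.

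Other text in the same section bears on how a failed tooth is examined:
- Preoperative, "immediate post-obturation, and follow-up radiographs will be viewed on the computer screen".
- There is a quality criterion: "The quality of previous treatment will be judged satisfactory if a well-condensed root filling extends to within 2 mm of the radiographic root apex".
- If pain or pressure persists, the endodontist assesses prognosis and decides whether the tooth is viable or should be extracted.
- A tooth that goes to extraction is examined for other possible causes of failure.
- Complications in general are to be handled case by case, and recall visits have their own form.

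On attribution, the section gives a success rate of about 86% for primary RCT and cautions that a failure cannot be assumed to be due to NDGP.

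**The concern.** The filler rule rests on a cause of failure written down before any tooth has failed. That goes further than the plan's own caution. Saying that failure may not be put down to NDGP leaves the question open, whereas the retreatment rule closes it in the material's favour. The trial's stated hypothesis is that NDGP does not worsen clinical outcome, so the protocol should not take that for granted in the teeth that fail.

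Two things are at stake. A patient whose tooth failed with an experimental filler would receive it again without anyone having to ask whether the filling contributed. And with 15 patients per arm, each failure is one of very few clinical observations on the material, so its attribution should not be settled beforehand.

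**Working it through.** **Step 1. Set the presumed causes beside the listed causes.** The rule presumes either extruded regular gutta-percha or insufficient instrumentation.

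| Cause named in the paragraph | Covered by the presumption? |
|---|---|
| Residual pulp | Yes (instrumentation) |
| Untreated narrow or curved canals | Yes (instrumentation) |
| Undetected anatomy | Yes (instrumentation) |
| Delayed restoration | No |
| Inadequate seal | No |

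Three of five listed causes fit and two do not. Extruded gutta-percha, the first presumed cause, is not in the list. Persistent radiolucency and infection are indications with no cause attached.

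**Step 2. Could the filling be involved?** Of the two causes outside the presumption, only inadequate seal could involve it. The plan does not say which seal is meant, and NDGP occupies only the middle third. A role is conceivable, no more. The Summary treats the filler as relevant to fit at the root wall ("potential decrease in void space between the NDGP"), the Study Protocol section accepts "persistent infectious bacteria or microleakage of the endodontically treated tooth" as a reason for later extraction, and NDGP is rolled into shape by hand.

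**Step 3. Does any assessment govern the choice of filler?**
- Radiograph review: records periapical status; no link to the filler.
- Quality criterion: no link to the filler.
- Perforation: bears on whether to retreat, not on the material.
- Prognosis check: decides between keeping and extracting the tooth.
- Cause evaluation: stated for extracted teeth only.
- Case-by-case handling: general wording, which does not displace a specific directive.

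None is tied to the choice.

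**Step 4. Scale.** The plan gives no figure to reproduce. Inputs: 15 patients in the NDGP arm (Summary); failure 14%, from 1 − 0.86 (Study Protocol section). Assumptions: one tooth per patient; 86% applies at 1 year; 25%, 50% or 100% of failures are retreated; a lower failure rate of 5%, in case the entry exclusions (such as complicated anatomy and periapical radiolucency) reduce failures.

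With p = failure rate × share retreated, the expected number is 15p and the chance of at least one is 1 − (1 − p)^15.

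| Failure | Share retreated | p | Expected teeth (15p) | At least one | Three or more |
|---|---|---|---|---|---|
| 14% | 25% | 0.035 | 0.525 | 1 − 0.965^15 = 0.414 | 0.014 |
| 14% | 50% | 0.07 | 1.05 | 1 − 0.93^15 = 0.663 | 0.083 |
| 14% | 100% | 0.14 | 2.1 | 1 − 0.86^15 = 0.896 | 0.352 |
| 5% | 25% | 0.0125 | 0.188 | 1 − 0.9875^15 = 0.172 | – |
| 5% | 100% | 0.05 | 0.75 | 1 − 0.95^15 = 0.537 | – |

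The 100% rows are an upper limit, because the plan sends some failures to extraction.

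**The case against.** The strongest reply is that this is loose drafting with no effect on any result. Failure is defined by symptoms, signs, radiographs and extraction for endodontic reasons, whatever the cause, and no planned analysis uses attributed cause in retreated teeth. That stands: no planned estimate is biased.

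Second, failed teeth are examined, and applying the list of indications already calls for a judgement about cause. This also stands, so it would be wrong to say that the plan never assesses them. What remains is narrower: no assessment is linked to the choice of filler.

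Third, a role for NDGP is speculative. The Summary expects void space to fall, not rise; the microleakage remark concerns extractions several years later and is not specific to NDGP; and the hand-rolled cone is then compacted warm with sealer. No document reports harm or a worse seal. This limits the concern but does not justify ruling the material out in advance.

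Fourth, keeping the assigned material at retreatment is a defensible choice. It is, but the plan defends it with an unsupported cause.

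A reader might also infer that control patients would be retreated with NDGP and so cross over. The text does not support that. The words *still* and *regular* point to the NDGP arm, and control teeth are assigned gutta-percha throughout. On this reading control crossover is zero, and the unnamed arm is a missing phrase.

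**Conclusion.** The point holds and is minor. The plan requires NDGP again in secondary RCT on a presumed cause that is narrower than its own list, and no existing assessment is tied to that choice. The effect is re-exposure of roughly 0 to 2 NDGP-arm patients (expected 0.2 to 2.1 of 15) and prejudged attribution of those failures. The chance that the rule is used at least once runs from 17% to 90%.

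These figures rest on the assumed retreatment shares, one tooth per patient, and either the plan's 86% applied at 1 year or an assumed 95%. The conclusion about the wording does not depend on them.

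A reader might infer that the between-arm failure comparison is biased, or that NDGP is a likely cause of failure. The documents support neither: the presumed cause does not enter the definition of failure, and nothing in them shows that NDGP impairs the seal.

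**What to change.** Delete the presumed-cause clause. In its place, state that:
- before a tooth in the NDGP arm is retreated, the endodontist records the likely cause of failure on the existing recall form, from the existing examination and the post-obturation and follow-up radiographs;
- a defective or poorly sealed filling is one of the permitted causes;
- NDGP may be used again only after that entry is made, and standard gutta-percha is used if the filling is implicated.

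Make the same entry for retreated control teeth and report cause descriptively by arm. Adding that the rule applies in the NDGP arm is a clarification of wording only.

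The 2 mm criterion should not carry the decision alone. Its length element concerns the apical third, which is gutta-percha in both arms, so it is not a specific test of the middle-third filling.

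The cost is a change of wording, one field on a form that already exists, and a few minutes per retreated tooth, with no new visit, procedure or staff. The drawback is that the entry is a subjective judgement and, at these numbers, descriptive only.

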
## **Study Protocol:**

[name] will recruit the patient for this study after the patient's referral to the UCLA endodontics department for root canal therapy. Informed consent will be obtained by [name] from all the patients that will be able to be taken home for patients to consider being part of this pilot study. We will stress to the patient that there will be an intended benefit and that we will be providing an incentive for joining this study (parking vouchers). The sample population will be screened and collected [name], M.S.,

Ph.D., D.D.S. All of the patients must be over 18 years of age when the treatment commences. Teeth will be excluded from this study if they had preoperative periodontal disease, prior non-surgical and surgical endodontic treatment, or if the apex/apices under investigation is/are not discernible in any of the periapical radiographs. The teeth that will be excluded from the analysis of the 'periapical status following treatment' are if: (1) they were not followed-up for at least 6 months, (2) if they were extracted for reasons not related to endodontic problems (for e.g. periodontal disease), (3) information on the periapical status during the time of extraction was not available.

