oxide-eugenol (Kerr Corporation, Orange, CA, USA). After the root canal treatment is done, the patient will be treated by [name], a general dentist for the restorative aspect of the procedure. Depending on how much tooth structure is left, he will decide which kind of build-up material to use and if a post is needed. The tooth will be restored with a crown for posterior teeth, or a composite filling for anterior teeth.

The goal is to follow-up all treated teeth 6 months and 1 year post-RCT. Appointment letters will be mailed to the patients 1 month prior to the follow-up dates. Patients, who failed to attend for recall, will be contacted with a personal courtesy call by the study team member (dentist on study team) and a more detailed explanation letter will be mailed to encourage them to attend follow-up appointments. If patients continue to not attend for recall, then the reasons provided by each patient (if provided) will be recorded. Recall appointments can be made as necessary other than the 6-month and 1-year follow-up appointments. Recall appointments will have their own specific form detailing the patient's reason and required procedure. Possible complications will be communicated to the patient prior to the study and will be dealt with on a case by case basis.

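### A tooth extracted for endodontic problems without a periapical record can be both a failed outcome and excluded from the periapical-status analysis, and the two exclusion wordings disagree

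*Combined protocol and SAP*

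**What the plan says.** All the relevant text is in the Study Protocol section of the combined protocol and SAP.

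- **Failure rule** (paragraph on risks and complications). When a tooth is extracted because of endodontic problems, for which pain, swelling, a sinus and a periapical lesion are given as examples, "the treatment will be considered as a failed outcome". No periapical record is required.
- **Later exclusion** (the next sentence). "Tooth extraction without any information on postoperative periapical status will be excluded from analysis". It names neither a reason for extraction nor a particular analysis.
- **Listed exclusions** (eligibility paragraph near the start of the section). Three kinds of teeth are "excluded from the analysis of the 'periapical status following treatment": rule (1), "1) they were not followed-up for at least 6 months"; rule (2), "if they were extracted for reasons not related to endodontic problems"; rule (3), "information on the periapical status during the time of extraction was not available".
- **Outcomes** (paragraphs on treatment success). There are two: absence of apical periodontitis, judged clinically and radiographically, and tooth survival. Strict success requires no pain, no clinical inflammation or swelling, and complete radiographic healing.

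No order of precedence between the failure rule and the exclusions is given. The Statistical Analysis section covers only tests of material properties and does not settle the point.

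**The concern.** The failure rule depends on why the tooth was extracted. The exclusions depend on what was recorded. The two conditions can hold together, and the plan does not say which then governs.

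The overlap falls on failures. Rule (2) already removes extractions unrelated to endodontic problems, so the only extractions rule (3) can add are those for endodontic or unknown reasons. For the endodontic ones the result is already known: a tooth extracted for persistent pain or swelling cannot meet the strict success definition, whatever a radiograph would have shown. Excluding it resolves no uncertainty. It takes a failure out of the denominator and raises reported periapical success.

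The differing wordings add a second problem: the same tooth can be classified differently depending on which paragraph the analyst follows.

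**Working it through.** There is no stated figure to reproduce: the documents give no extraction rate, margin or power calculation. The main check is to set the rules side by side.

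Here, periapical record means radiographic or examination findings beyond the reason for extraction.

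| Extracted tooth | Failure rule | Later exclusion sentence | Listed rules |
|---|---|---|---|
| A. Endodontic reason, no postoperative periapical record | Failure | Excluded | Excluded by (3) |
| B. Endodontic reason, record at 6 months, none at extraction | Failure | Not excluded | Excluded by (3) |
| C. Endodontic reason, record at extraction | Failure | Not excluded | Not excluded by (2) or (3) |
| D. Non-endodontic reason | Does not apply | Depends on record | Excluded by (2) |
| E. Unknown reason, no record | Does not apply | Excluded | Excluded by (3) |

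Row A meets the failure rule and both exclusions. Row B is a failure under the complications paragraph and excluded under the eligibility paragraph. Rows C to E show no conflict with the failure rule.

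**Size, for illustration only.** Inputs: 15 patients per arm (Summary), taken as one tooth each; about 86% success for primary treatment (complications paragraph); number of affected teeth assumed.

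1. Expected failures per arm: 15 × (1 − 0.86) = 2.1, so take 2.
2. Failures kept: 13/15 = 86.7%.
3. One failure excluded: 13/14 = 92.9%, a rise of 6.2 points.
4. For scale, the standard error of a between-arm difference at 86% is √(2 × 0.86 × 0.14 / 15) = 0.127, so the shift is 0.062/0.127 = 0.49 of one standard error. No clinical test is specified against which to set this.
5. Step 3 drops half of that arm's failures. For smaller shares, let p be the proportion of all teeth that are failures and are excluded. Expected reported success is 0.86/(1 − p), and the chance of at least one such tooth in 30 is 1 − (1 − p)^30.

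| Assumed p | Share of the 14% failures | Expected reported success | Chance of at least one in 30 |
|---|---|---|---|
| 0.5% | 3.6% | 86.4% | 14% |
| 1% | 7.1% | 86.9% | 26% |
| 2% | 14.3% | 87.8% | 45% |

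The average effect over this range is 0.4 to 1.8 points. The 6.2 points is what one such tooth does if it occurs in an arm with two failures.

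**The case against.** The strongest reply is that the two sentences can be read as dividing the cases. Apical periodontitis is assessed clinically as well as radiographically, and pain, swelling and a sinus are clinical evidence. If the reason for extraction itself counts as periapical information, a known endodontic extraction is always a failure, and the exclusion reaches only teeth about which nothing is known. This reading is possible, and it would empty row A. But periapical information is not defined, and the paragraph on viewing radiographs classifies preoperative periapical status by the periodontal ligament and lesion. Nor does it remove the mismatch between status at extraction and any postoperative information. What stands is that row A is conditional on what periapical information means.

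Other points in the plan's favour also stand. Extra visits for infection or pain, extra radiographs for persistent discomfort, evaluation of prognosis, and examination of the extracted tooth make a missing record unlikely. Retreatment is allowed, so many failures may be retained teeth.

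A reader might infer more than the documents support:

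- **That known failures are lost through non-attendance or pregnancy.** For persistent non-attenders, "then the reasons provided by each patient (if provided) will be recorded"; these are reasons for missing recall, not for extraction. In pregnancy "the radiographic examination will be deferred until after delivery", but nothing says the clinical examination is deferred too. Neither shows a known failure being dropped.
- **That rule (1) drops early endodontic extractions.** It does not say so and is most naturally a rule about loss to follow-up.
- **That both outcomes are distorted.** The listed exclusions are confined to the periapical analysis. Tooth survival is a separate outcome, for which an extraction is itself the event.
- **That the comparison between arms is biased.** The rules are the same in both arms, and nothing shows that affected teeth would fall more in one.

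**Conclusion.** The rules are wrong as written, and the issue is minor. Rule (3) and the later exclusion sentence make no exception for a tooth that the plan itself counts as failed, and they set different conditions for exclusion. The row A conflict rests on one assumption, that periapical information means a radiographic or examination record beyond the reason for extraction. On that assumption, applying the exclusion raises reported periapical success. The disagreement between the two exclusion wordings does not need that assumption to the same degree: it remains even if the later sentence is read as reaching only teeth about which nothing is known.

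The effect is limited to the periapical-status analysis. Its size cannot be derived from the documents and is probably small on average, although in arms of 15 a single tooth is visible in the reported rate. The documents do not support a claim that overall treatment success is inflated, or that the comparison of the two filling materials is shifted in a known direction.

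**What to change.** 1. State that, in the periapical analysis, a tooth known to be extracted for endodontic problems within the 1-year follow-up counts as a failure with or without a radiograph, and that this takes precedence over the exclusions in both the eligibility and the complications paragraphs. The time limit matters because the complications paragraph also mentions extractions several years later.
2. Limit the missing-status exclusion to extractions whose reason is unknown, and use one wording in both paragraphs. Rule (2) continues to cover non-endodontic extractions.
3. State that these exclusions do not apply to tooth survival, and report the number of excluded teeth and the reasons by arm.

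The cost is a few sentences of outcome definition, best settled before outcomes are classified. No treatment or visit changes. The downside is that reported periapical success may be slightly lower.

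### The exclusion of extractions without periapical information is stated with two different scopes, and on the wider one known tooth losses would drop out of tooth survival

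*Combined protocol and SAP*

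**What the plan says.** All the relevant text is in the Study Protocol section.

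- **Outcomes.** The paragraph on treatment success says: "Treatment success will be evaluated based on two outcome measurements: (1) absence of apical periodontitis via clinical and radiographic evaluation, (2) tooth survival".
- **Limited exclusion.** The eligibility paragraph opens a three-item list with "The teeth that will be excluded from the analysis of the 'periapical status following treatment' are if". Its third item covers teeth for which "information on the periapical status during the time of extraction was not available".
- **Unlimited exclusion.** The paragraph on risks and extraction says: "Tooth extraction without any information on postoperative periapical status will be excluded from analysis". It names no outcome.
- **Extraction as failure.** Just before that sentence, the same paragraph says of a tooth extracted for endodontic problems "such as persistent pain, swelling, sinus or periapical lesion, the treatment will be considered as a failed outcome".

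The Statistical Analysis section deals only with mechanical properties of the material. No section defines tooth survival, gives its analysis set or says how extractions enter it. The Summary sets the arm sizes: "15 patients for the control, 15 patients with NDGP".

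**The concern.** An extraction is the event that tooth survival exists to count. Once it is known that the tooth is gone, the outcome is known, whether or not anyone recorded the state of the periapical tissues. A rule that drops extractions for lack of periapical information is understandable for the periapical outcome, where the value really is missing. For survival it would delete observed events.

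This matters more here than in a larger trial. The Summary's rationale is that a stronger filler might reduce the need for extraction, and its hypothesis is that the new material does no clinical harm. With 15 teeth per arm, one or two deleted losses can take an arm's survival to 100%.

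**Working it through.** **1. Compare the two exclusion statements.**

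| | Eligibility paragraph | Risks and extraction paragraph |
|---|---|---|
| Trigger | No periapical information at the time of extraction | No postoperative periapical information at all |
| Scope | Periapical status analysis only | Analysis, with no outcome named |
| Effect on tooth survival | None | Removes the tooth, if applied as worded |

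The rule is essentially the same, but the scope differs and the trigger differs slightly.

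**2. Look for text that settles the scope.** There is none. Survival is named but not defined, and the Statistical Analysis section does not mention it. The risks paragraph also overlaps with itself: a tooth extracted for persistent pain with no periapical record meets both the failed-outcome sentence and the exclusion sentence.

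**3. Size of the effect if the unlimited sentence is applied to survival.** The plan states no figure to reproduce. Inputs: n = 15 per arm (Summary); e = extractions in the arm; x = those excluded. Both e and x are illustrative.

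- All known extractions counted: survival = (15 − e)/15.
- x extractions excluded: survival = (15 − e)/(15 − x).

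| e | x = 0 | x = 1 | x = 2 | x = 3 |
|---|---|---|---|---|
| 1 | 14/15 = 93.3% | 14/14 = 100% | – | – |
| 2 | 13/15 = 86.7% | 13/14 = 92.9% | 13/13 = 100% | – |
| 3 | 12/15 = 80.0% | 12/14 = 85.7% | 12/13 = 92.3% | 12/12 = 100% |

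**4. Range under assumed rates.** Let q be the extraction rate and m the share of extractions without periapical information. The documents give neither. I assume q from 5% to 14% and m from 25% to 100%. The 14% is the complement of a success rate that the risks paragraph cites ("Most studies say that primary RCTs have about a 86% success rate"). It is borrowed as an upper bound and is not an extraction rate.

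- Expected reported survival is approximately (1 − q)/(1 − qm).
 - q = 5%: true 95%; reported 0.95/0.9875 = 96.2% at m = 25%, rising to 100% at m = 100%.
 - q = 14%: true 86%; reported 0.86/0.965 = 89.1% at m = 25%, rising to 100% at m = 100%.
- Chance that at least one event is lost among 30 patients: 1 − (1 − qm)^30.
 - Lowest: 1 − 0.9875^30 = 31%.
 - Highest: 1 − 0.86^30 = 99%.

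**5. Effect on the comparison of arms.** The direction is not fixed.

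- Two losses on the nanodiamond material and none on control, both excluded: 86.7% v 100% becomes 100% v 100%, and a possible harm is hidden.
- The same losses on control instead: a possible benefit is hidden.
- One loss in each arm, one of them excluded: 93.3% v 93.3% becomes 100% v 93.3%, a difference of 6.7 points where there was none.

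**6. If the limited scope governs,** x = 0 for survival in every row, and no survival event is lost.

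**The case against.** The strongest reply is that the limit is already in the plan. The eligibility paragraph holds the formal exclusion list, and the later sentence looks like a short restatement of its third item. Its own criterion is periapical status, and the sentences around it concern failure and success of the root canal treatment, not survival. That reading is plausible, and on it survival is untouched. It stands as a likely intention, but no text makes it the rule.

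The trigger may also be narrow. The later sentence applies only where no postoperative periapical information exists. The protocol plans radiographs immediately after obturation and at follow-up, so a tooth seen at 6 months and lost afterwards might not qualify. This could make the affected group small. However, the protocol does not say whether the immediate film counts, and the eligibility paragraph looks instead to the time of extraction.

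Three stronger inferences are tempting, and the documents do not support them:

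- **That the plan has decided to drop known losses from survival.** The limited list contradicts this. The loss is conditional on the unlimited sentence prevailing.
- **That the rule favours the nanodiamond arm.** It applies to both arms and can distort the comparison either way. That it would fall mainly on teeth extracted outside the study clinic is likewise inference, not text.
- **That survival must count extractions of every cause.** The protocol does not say so. The eligibility list already separates extractions unrelated to endodontic problems, and cause-specific survival is also defensible.

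Finally, the absence of any written survival analysis is the larger gap, and filling it would settle this point too. That is true, but it does not make the conflicting sentence harmless in the meantime.

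**Conclusion.** The two statements conflict in scope, and nothing in the plan resolves the conflict for tooth survival. Applied as worded, the later sentence would remove observed losses from a named outcome and bias survival upward in whichever arm they occur. With 15 teeth, one exclusion moves survival by roughly 5 to 8 percentage points across the cases tabulated (12/15 to 12/14 is 5.7 points; 12/13 to 12/12 is 7.7). On the narrower scope the effect is zero.

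The percentages are illustrations. They depend on assumed numbers of extractions and of missing records, and the 100% figures require every extraction in the arm to lack periapical information. The finding is a wording conflict that can produce a wrong result, not a demonstrated bias in the planned analysis. It should be corrected because the correction is short and removes the risk.

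**What to change.** In the risks and extraction paragraph, replace the unlimited wording with *excluded from the analysis of periapical status only*. Add one sentence: no known extraction is dropped from tooth survival because periapical information is missing. Report extractions by arm and cause, so that all-cause and endodontic-cause survival can both be read and neither definition has to be imposed by the exclusion rule. While making the change, reconcile the two triggers (information at the time of extraction, or any postoperative information).

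The cost is a sentence or two and one small table. Cause of extraction is already needed to apply the eligibility paragraph's exclusion of teeth lost for unrelated reasons. The one downside is that the survival figure may be slightly less favourable. If the limited scope was always intended, the results do not change.
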